5.2. VISIT SCHEDULE

The study will be performed over 24 to 29 sessions:

- 1) Visit 1(Screening visit): Baseline = 3-12 months after the stroke. The purpose of this visit is to obtain informed consent for the study (if not previously obtained) and to screen subjects for inclusion and exclusion criteria.
- 2) Visit 2: Baseline assessment. The purpose of this visit is to establish the baseline of injury, motor status and NBS parameters (Localization of cortical motor representation area of the target muscle to which therapeutic rTMS will be subsequently delivered, see appendix A). Subjects will also undergo a structural MRI. The subject will then be randomized to either rTMS or to sham treatment. The baseline visit may if necessary take place on 2 separate days.

- 3) Visits 3-20: During these visits the patient will undergo standardized task-oriented motor rehabilitation of the hand. In addition the patient will receive the rTMS therapy according to the protocol of the group she/he was randomized into during visit 1. The visits will take place during a 6 week period, three visits per week. During each week the visits will take place each on a separate day and a maximum of two visits will take place on consecutive days.
- 4) Visit 21: End of the task-oriented motor rehabilitation. The purpose of the visit is to establish the extent of recovery that has occurred during the rehabilitation. The visit will take place 5-10 days after the last rTMS/rehabilitation session and includes functional motor testing).1-2 visits may be needed to complete assessment.
- 5) Visit 22: 1month (±5 days) after the end of the rehabilitation therapy. The purpose of the visit is to determine whether any changes in motor function have occurred within 1 month of ending therapy. The assessment includes functional motor testing. 1-2 visits may be needed to complete assessment.
- 6) Visit 23: 3 months (±5 days) after end of the rehabilitation therapy. The purpose of this visit is to determine whether any changes in motor function or NBS parameters have occurred within 3 month of ending therapy. The assessment includes functional motor testing. In patients experiencing a new stroke, only the data prior to the event will be used in the analysis. 1-2 visits may be needed to complete assessment.

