5.2.5 Outcome Assessments

The visits will take place 5-10 days, 1 month, 3 months and 6 months after the completion of the study treatment visits. The visits will last approximately 3 hours and consist of the following functional tests which will be performed at each and every outcome assessment visit:

- The National Institutes of Health Stroke Scale (NIHSS)
- Fugl Meyer (FM)
 - The Fugl-Meyer test is the primary outcome measure for the trial.
- ARAT
- EQ-5D

5.2.6 Occupational therapy, physiotherapy and home exercise program during the active treatment and follow-up periods of the trial

Occupational therapy:

During the 6 weeks active treatment period of the trial (visits 3-20) the patients are not allowed any other occupational therapy except that provide in the trial. After the active treatment period during the 6 month follow-up period of the trial, patients are allowed occupational therapy. The hours of therapy will be documented. Patients will be queried once every 2 weeks until the final outcome assessment visit at 6 months after end of active trial treatment, either when they visit the study site or they will be called and queried.

Physical therapy:

Patients are allowed participation in physical therapy for the full trial duration including during the active treatment period of the trial (visits 3-20). However, the hours of therapy and time of use of the affected upper extremity in treatment sessions will be documented. Patients will be queried once every 2 weeks until the final outcome assessment visit at 6 months after end of active trial treatment, either when they visit the study site or they will be called and queried.

Home exercise program:

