6.0 ANALYSIS PLAN

The results of functional motor tests at end of rehabilitation (5-10 days post treatment) and at 1, 3 and 6 months after the end of rehabilitation will be compared to the results obtained at baseline to determine the functional recovery if any that has occurred. The results of patients randomized into separate groups will be compared to each other to determine the effect of rTMS.

The primary analysis population will be the intent-to-treat (ITT) population. In addition, a separate analysis will be conducted on the per protocol (PP) population.

Primary outcome measure for the trial is the Upper-extremity Fugl-Meyer score.

The beneficial effect of 1Hz NBS guided rTMS will be established if a statistically significantly greater proportion of patients receiving NBS-rTMS attain clinically important improvement in the primary outcome measure than patients receiving sham-rTMS between baseline and 6 months post-treatment.

The size of the treatment effect will be measured by the odds ratio parameter which is defined as

$$OR = \frac{P_{TRT} / (1 - P_{TRT})}{P_{REF} / (1 - P_{REF})}$$

where P_{TRT} and P_{REF} denote the proportion of subjects with clinically significant change from baseline in Fugl-Meyer score, in the treatment and reference groups respectively.

The null hypothesis is H_0 : OR = 1 and the two-sided alternative hypothesis is H_1 : $OR \neq 1$.

The proportion of responders in each treatment group will be summarized, along with the estimated odds ratio, the 95% confidence interval for OR, and the Wald Chi-square test p-value. The primary analysis will be performed on the ITT, and on the PP population as a sensitivity analysis.

Secondary outcome measures for the trial are ARAT test, , NIHSS, and EQ-5D.

Descriptive statistics will be summarized by treatment and visit. Absolute difference (in points) in improvement will be summarized for both treatment groups between baseline and 5-10 days and 1, 3 and 6 month follow-up visits and the treatment groups compared via a two-way ANOVA.

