6.4 STRATA AND COVARIATES

The primary efficacy analysis will be stratified by length of time after stroke (3-6 months vs. 6-12 months).

Additional covariate analyses will model the primary endpoint (a binary response of UEFM score improvement), absolute changes (in points) in the tests of motor function (UEFM, and ARAT) using hours of occupational therapy outside the trial and overall hours of therapy (occupational, physical, and home exercise) as covariates during treatment phase and over the entire 6 months of follow-up.

All covariate analysis will be performed for both ITT and PP population.

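### The section 6.4 therapy-hours models condition on post-randomisation data, so an arm coefficient from them need not be the effect of randomised treatment; the supportive adjustment should use baseline scores

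*Combined protocol and SAP*

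**What the plan says.** Section 6.4 first settles the main analysis: "The primary efficacy analysis will be stratified by length of time after stroke (3-6 months vs. 6-12 months"). It then turns to supportive models. "Additional covariate analyses will model the primary endpoint", together with change in ARAT and in UEFM, "using hours of occupational therapy outside the trial and overall hours of therapy (occupational, physical, and home exercise) as covariates during treatment phase". The counting window does not close when treatment ends; the same sentence extends it with the words "and over the entire 6 months of follow-up". Both the ITT and the PP population are to be used.

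On timing, section 5.2 places allocation at the end of the baseline visit (Visit 2): "The subject will then be randomized to either rTMS or to sham treatment". Treatment runs from Visit 3 to Visit 20, and the primary endpoint is read at Visit 24.

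On the hours themselves, section 5.2.6 says that in the six treatment weeks "the patients are not allowed any other occupational therapy except that provide in the trial". Later the rule changes: "After the active treatment period during the 6 month follow-up period of the trial, patients are allowed occupational therapy". Physical therapy is permitted throughout. The patient's own therapist may alter the follow-up home programme to suit clinical need. Hours are collected by fortnightly query until the six-month visit.

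On baseline scores, section 5.2.2 schedules UEFM and ARAT before allocation. Section 6.0 summarises change in points and has "the treatment groups compared via a two-way ANOVA". No supplied section names either baseline score as a covariate. Section 6.1 sends detailed methods to a separate SAP, which is not among the documents.

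**The concern.** A covariate measured before allocation cannot be affected by treatment; therapy hours counted after allocation can. A patient who recovers well may be discharged from therapy sooner, or may be encouraged to do more. Either way, hours can be a route by which treatment acts or a marker of how recovery is going. Comparing arms at equal hours then answers a different question from the randomised comparison, and can shrink or enlarge the apparent effect.

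The models cover the primary endpoint and both motor scales. Section 6.4 does not say what their arm coefficient would mean. Meanwhile the adjustment that would help a trial with about 30 patients per arm, on the baseline value of the score, is not named.

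**Working it through.** **1. The plan's own figure.** Section 6.1 states 81% power for 60 patients, and 96% when active-arm data are borrowed (118 vs 30). I used the pooled-variance normal approximation for two proportions, two-sided 0.05, without continuity correction:

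power = Φ{(|p1 − p2| − 1.96·√[p̄(1 − p̄)·2/n]) / √[p1(1 − p1)/n + p2(1 − p2)/n]}

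- 84% vs 50%, n = 30: (0.34 − 1.96 × 0.1214)/0.1132 = 0.90, giving 81.6%.
- 72% vs 36%, n = 30: (0.36 − 1.96 × 0.1287)/0.1200 = 0.90, giving 81.6%.
- 118 vs 30, same method with unequal arms: 96.1% and 95.9%.

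The stated power reproduces. It belongs to an analysis without hours in it, so nothing below changes it.

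**2. The shift from adjusting for hours.** Let τ be the total effect of randomised treatment on the outcome, δ the mean arm difference in hours (active minus sham), and β the within-arm slope of outcome on hours. In a linear model with arm and hours, the arm coefficient is τ − βδ, so the shift is −βδ. If δ = 0 or β = 0, the shift is zero.

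The documents give neither δ nor β. Assumed values: UEFM change SD about 8 points, hours SD about 10, β = ±0.2 points per hour (a within-arm correlation of about 0.2 × 10/8 = 0.25), and δ of 0, 5 or 10 hours in size. The pilot mean changes in section 1.1 give a scale: 13.8 − 7.1 = 6.7 points.

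- 5 hours: 0.2 × 5 = 1.0 point; 1.0/6.7 = 15%.
- 10 hours: 0.2 × 10 = 2.0 points; 2.0/6.7 = 30%.

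A simulation with 60 patients and 6,000 replicates per row agrees with the formula:

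| Scenario | δ | β | −βδ | Adjusted estimate, true effect 6.7 | Adjusted estimate, true effect 0 | Rejection rate, true effect 0 |
|---|---|---|---|---|---|---|
| Hours do not differ by arm | 0 | +0.2 | 0 | 6.68 | 0.00 | 4.8% |
| Hours affect outcome | +10 | +0.2 | −2.0 | 4.76 | −2.00 | 13.4% |
| Hours affect outcome | −10 | +0.2 | +2.0 | 8.69 | 1.98 | 13.5% |
| Hours inert, weaker patients do more | −10 | −0.2 | −2.0 | 4.67 | −1.97 | 13.8% |
| Hours inert, weaker patients do more | −5 | −0.2 | −1.0 | 5.65 | −0.98 | 7.8% |

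Without the hours term, the mean estimates stayed at 6.67 to 6.75 when the true effect was 6.7, and the test rejected 4.2% to 5.4% of the time when it was zero. In the two rows where hours act on outcome, the adjusted coefficient is a direct effect, a real quantity but not the total effect of allocation. In the last two rows it is neither.

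**3. Outside occupational therapy in the treatment phase.** Section 5.2.6 bars it, and section 4.2 excludes patients who plan it. This covariate should be near zero for compliant patients and would mainly record deviations. Overall hours still vary.

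**4. Baseline score.** With equal variances at baseline and six months and correlation ρ between them, the variance of the treatment estimate under baseline adjustment, relative to a simple change-score comparison, is (1 − ρ²)/[2(1 − ρ)] = (1 + ρ)/2. For assumed ρ of 0.3, 0.5 and 0.7 this is 0.65, 0.75 and 0.85. The formula applies to the change outcomes, not to the binary response.

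**The case against.** The case on the other side is substantial.

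- The hours models are called additional, and no success rule rests on them. Section 6.1 gives the robustness role to the non-Bayesian analysis of E-FIT data alone, and section 6.0 makes the PP analysis the sensitivity analysis. A reader might infer that the hours models will be offered as support for the main result; no passage says so.
- Section 6.4 does not write out a treatment term. The models could simply describe how hours relate to outcome. The treatment term is my inference from their purpose.
- Patients, therapists and assessors are blinded. If treatment does nothing, there is little besides chance or unblinding to make hours differ by arm, and then the shift is small or zero.
- Co-therapy in follow-up is uncontrolled and deliberately recorded. Looking at it is legitimate, so dropping the hours models altogether would go too far.
- Time since stroke is a pre-randomisation factor and already stratifies the primary analysis, so it would be wrong to say that no baseline covariate is used. Baseline scores also enter through the change scores. The separate SAP may name them as covariates.

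All of this limits the point without removing it. If treatment works, blinding does not stop recovery from altering hours. Section 6.4 neither labels these models exploratory nor says how an arm coefficient is to be read.

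**Conclusion.** The point holds in a limited form. If the hours models include a treatment term, and if hours differ by arm and relate to outcome within arm, the arm coefficient is not the effect of randomised treatment. The departure is −βδ: zero without an arm difference in hours, and about 1 to 2 UEFM points for 5 to 10 hours at 0.2 points per hour. With a true total effect of zero, a nominal 5% test then rejects about 8% (5 hours) or 13 to 14% (10 hours) of the time. These sizes rest on assumed inputs and a linear model, and do not carry over directly to the binary response.

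Two stronger readings are not supported. A reader might conclude that the trial's main result is biased; it is not adjusted for hours, so the success rule and the 81% and 96% power stand. A reader might also take the absence of baseline UEFM and ARAT as a source of bias; in a randomised comparison it costs precision and leaves chance imbalance uncorrected, and it is established only for the supplied text.

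**What to change.** In section 6.4, and in the separate SAP so that the two agree:

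1. Make the supportive adjusted analysis of UEFM response, UEFM change and ARAT change use pre-randomisation covariates: the baseline value of the score, the time-since-stroke stratum, and site where numbers allow (60 patients over 5 centres is 12 per site on average).
2. Summarise therapy hours by arm, separately for the treatment phase and follow-up, with outside occupational therapy in the treatment phase shown as deviations.
3. Keep any hours-adjusted model as exploratory, write out its terms, and state that its arm coefficient is not an estimate of the randomised treatment effect.

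The cost is wording only. Baseline scores, stratum, site and hours are all already collected.

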6.5 SIGNIFICANCE LEVEL

Unless otherwise noted, all statistical analyses will be conducted with a significance level (α) of 0.05 and utilize two-sided testing.

Since the ARAT test has potential to be used for labelling purposes, a Bonferroni adjustment will be employed. A significance level (α) of 0.025 will be used for this secondary analysis only. All other secondary analyses will use $\alpha = 0.05$ as they are not to be used for any labeling purpose.

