The statistical analysis of the present trial will be performed in two phases. The Bayesian analysis of the E-FIT data combined with data borrowed from the active trial arm of the previously completed NICHE trial (NCT02089464) will be the primary efficacy analysis. Non-Bayesian analysis of the E-FIT trial data only will be performed to demonstrate robustness of the result. Detailed methodology for the analyses is described in a separate statistical analysis plan (Document NX103391 EFIT Statistical Analysis Plan, version 1.0, dated 06 August 2018).

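### Section 6.5 invokes Bonferroni for a possible ARAT labelling claim but lowers only ARAT (to 0.025); if the frequentist UEFM test at 0.05 is the primary, the two claims share a bound of 0.075

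*Combined protocol and SAP*

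**What the plan says.** Section 6.5 sets a general level "of 0.05 and utilize two-sided testing" unless something else is noted. It then makes one exception: "Since the ARAT test has potential to be used for labelling purposes, a Bonferroni adjustment will be employed", with a level "of 0.025 will be used for this secondary analysis only". The remaining secondary analyses stay at 0.05 "as they are not to be used for any labeling purpose". Nothing lowers the level of the UEFM responder test. Section 6.0 reports its odds ratio with a 95% confidence interval, and the sample size in section 6.1 is computed at 0.05.

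Two sections describe the primary analysis differently. Section 6.0 sets out the odds ratio and Wald test and continues: "The primary analysis will be performed on the ITT, and on the PP population as a sensitivity analysis". Section 6.1 says that the Bayesian analysis borrowing NICHE active-arm data "will be the primary efficacy analysis", and that "Non-Bayesian analysis of the E-FIT trial data only will be performed to demonstrate robustness of the result". It gives no alpha or posterior threshold for the Bayesian analysis and defers further: "Detailed methodology for the analyses is described in a separate statistical analysis plan".

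**The concern.** Bonferroni divides one error rate among the members of a family. The ARAT level is exactly half of 0.05, and ARAT is the only secondary endpoint that section 6.5 links to labelling, so the natural second member is the UEFM primary. A two-test Bonferroni adjustment would then put both tests at 0.025. Halving one and leaving the other at 0.05 does not hold the pair at 0.05.

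A fixed testing order would also give control, with UEFM at the full 0.05 and ARAT examined only after it succeeds. No section states such an order. Section 6.0 bases the trial's conclusion of benefit on UEFM responders alone, but does not say what a significant ARAT result may be used for if UEFM fails.

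Labelling is the plan's own reason for adjusting. As written, a reader of section 6.5 cannot tell whether ARAT could enter the label after a failed primary, or which analysis would decide that the primary had failed.

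**Working it through.** **Inputs.** UEFM level 0.05 two-sided and ARAT level 0.025 (section 6.5); about 30 patients per arm (section 5.2.3); responder rates 84% vs 50% and 72% vs 36%, and stated power of 81% and 96% (section 6.1); NICHE sham rate 65% (section 1.1). The UEFM–ARAT correlation is not given, so a range is assumed.

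**Step 1: reproduce the plan's figures.** 0.05/2 = 0.025, which is the ARAT level. To confirm that UEFM is planned at the full 0.05, use the pooled-variance power formula for two proportions with n per arm:

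power = Φ{ [ |p1 − p2| − z·√(2·p̄·q̄/n) ] / √[(p1q1 + p2q2)/n] }

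For 72% vs 36%, n = 30 and z = 1.96: (0.36 − 1.96 × 0.1287)/0.12 = 0.898, giving 81.5%. For 84% vs 50% the result is 81.6%. The stated figure is 81%. For 118 vs 30 the results are 95.9% and 96.1%, against the stated 96%. At 0.025 the same calculations give about 72.5% (30 vs 30) and 92.7% to 93.5% (118 vs 30). The plan's power therefore rests on UEFM at 0.05.

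**Step 2: bound for the pair, with the frequentist UEFM test as primary.** 0.05 + 0.025 = 0.075. With independent tests: 1 − 0.95 × 0.975 = 0.07375. With both at 0.025 the bound would be 0.050, or 0.0494 if independent.

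**Step 3: correlated tests.** Bivariate normal, both nulls true, r = assumed correlation of the two test statistics. The benefit tails are 0.025 (UEFM) and 0.0125 (ARAT), with bound 0.0375.

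| r | At least one false claim, two-sided | At least one false benefit claim | False ARAT benefit, primary failed |
|---|---|---|---|
| 0 | 0.0737 | 0.0372 | 0.0122 |
| 0.4 | 0.0710 | – | – |
| 0.5 | 0.0694 | 0.0347 | 0.0097 |
| 0.62 | 0.0668 | – | – |
| 0.8 | 0.0609 | 0.0305 | 0.0055 |

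The last two columns differ by the UEFM benefit tail: 0.0122 + 0.025 = 0.0372, for example. At r = 0 the last column is 0.0125 × 0.975 = 0.0122.

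An r of 0.8 is about the most that is possible. If the UEFM change is normal and is cut at responder rate p, the statistic correlation cannot exceed φ(c)/√(p(1 − p)), where c is the cut point. This is 0.779, 0.798 and 0.777 at p = 36%, 50% and 65%.

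**Step 4: simulation at the trial's size.** 400,000 trials per cell, 30 per arm, unstratified Wald test on the log odds ratio at 0.05, two-sample t-test for ARAT at 0.025. Entries are for null responder rates of 36% / 50% / 65%.

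| Assumed patient-level correlation | At least one false two-sided claim | False ARAT benefit, primary failed |
|---|---|---|
| 0 | 0.068 / 0.076 / 0.067 | 0.0120 / 0.0123 / 0.0119 |
| 0.5 | 0.066 / 0.073 / 0.066 | 0.0108 / 0.0105 / 0.0107 |
| 0.8 | 0.061 / 0.067 / 0.060 | 0.0085 / 0.0080 / 0.0089 |

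The Wald test's simulated size was 0.043 to 0.052, so one entry slightly exceeds the nominal bound.

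**Step 5: the Bayesian analysis as primary.** Let x be its type I error, which the document does not give. The bound is x + 0.025: 0.05, 0.075 or 0.125 at assumed x of 0.025, 0.05 or 0.10. It is within 0.05 only if x is at most 0.025.

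**The case against.** The strongest reply is that section 6.1 is the more explicit statement of the primary analysis. It makes the Bayesian analysis primary and the trial-only analysis a robustness check, so the 0.05 of the Wald test need not be the primary's error rate. That is fair: 0.075 holds only on the section 6.0 reading, and otherwise the total is unknown. An unknown total does not show that the named adjustment works.

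Second, the two-test family at 0.05 is inferred. Section 6.5 could mean only a stricter threshold for one secondary, and it says no more than that ARAT might be used for labelling. This also stands as a limit. But the section names Bonferroni, uses half of 0.05, and exempts the other secondaries because they have no labelling use.

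Third, the separate SAP is the natural place for a testing order and may contain one. That cannot be excluded. Since the protocol itself sets the ARAT level and gives labelling as the reason, the condition for that use belongs there too.

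Fourth, two-sided figures count results favouring sham, which cannot support a benefit label. Correct: the benefit-only rate is 0.0305 to 0.0372 against 0.025, and the part that a testing order would remove is at most about 0.012.

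Finally, the simulation omits the stratification of section 6.4 and replaces the two-way ANOVA of section 6.0 with a t-test. It is a rough check. The conclusion rests on Steps 2 and 3.

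**Conclusion.** The point holds. The stated levels do not deliver the Bonferroni control that section 6.5 names. If the frequentist UEFM test is the primary, the two-sided bound is 0.075, and the rate is about 0.061 to 0.074 over the correlations considered. All of these exceed 0.05. The practical excess is modest: a false ARAT benefit claim beside a failed primary has probability 0.0055 to 0.0122. The primary test and the sample size are not affected.

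This rests on four assumptions: the family is UEFM and ARAT at 0.05, no testing order is stated elsewhere, both null hypotheses are true, and ARAT is tested once, at 6 months. Section 6.0 also compares groups at 5–10 days, 1 month and 3 months, which is not counted here. If the Bayesian analysis is the primary, the document does not allow the total to be calculated. Confidence is medium, mainly because the separate SAP was not available.

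**What to change.** Add one sentence to section 6.5 and a matching line in the separate SAP, for example: *The ARAT change from baseline to 6 months (ITT) may support labelling only if the named primary efficacy analysis succeeds; otherwise it is descriptive.* Name the analysis that decides this: the Bayesian borrowing analysis of section 6.1 or the trial-only Wald test of section 6.0. The 6-month time point and ITT population only repeat what sections 3.2 and 6.0 already indicate. If the SAP already has this order, repeat it in section 6.5.

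With this condition, the family-wise error is at most the larger of 0.025 and the type I error of the deciding analysis. Control at 0.05 therefore holds provided that type I error is at most 0.05, which would need to be shown if the Bayesian analysis decides. ARAT can stay at 0.025, and primary alpha and power are unchanged.

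The cost is that no ARAT labelling claim is possible after a failed primary. With the stated 81% primary power and an assumed 80% ARAT power, the chance of blocking a true ARAT claim is 0.80 × 0.19 = 0.152 if the tests are independent, and 0.117 or 0.092 at assumed statistic correlations of 0.4 or 0.62. The alternative, both tests at 0.025, is dearer: trial-only power falls from about 81.5% to 72.5%, and about 36 per arm would be needed to restore 81%.
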